8 STUDY ASSESSMENTS AND PROCEDURES

8.1 ENDPOINT AND OTHER NON-SAFETY ASSESSMENTS

The set of research measures will be conducted at Baseline 1, , Time 1, Time 2, Time 3, Time 4, and Time 5 (see the Schedule of Activities in section 3.1) for residents, families, and staff. The MOP has all of the CRFs in the appendices.

Residents:

Data will be collected by trained data collectors. Training will include:

DCs will consist of audiology students from the University of Pittsburgh, and the DSC [name]. These students have experience in hearing testing and interviewing in their clinical training which makes them ideal data collectors in this study. In addition, they have experience with geriatric populations and managing communication with individuals with communication challenges. Since June 2020, they also have experience using appropriate PPE and following strict sanitation guidelines related to clinical interactions. These same guidelines will be followed in resident interactions to ensure safety. Training of the DC's will include:

- Virtual audiometer simulation to ensure accuracy in completing Pure Tone Hearing Surveys. Adequate accuracy is defined as establishing thresholds within +/- 5 dB from the target air conduction threshold across four frequencies (500, 1000, 2000, 4000 Hz) in 10 simulation cases. The cases are set to have a variety of patient response types to mimic what the DC's will experience on site.
- Pure tone hearing surveys on 5 classmates will allow for practice with equipment placement and testing in a real environment (rather than simulated).
- The DSC will train the DC's in the use of the iPad interface with the REDCap data collection system. The DC's will collect practice data on two individuals using the interface. Data includes consent, demographics, and two surveys (Hearing Specific Health Related Quality of Life and Satisfaction with Social Participation).
- Practice interviewing will be completed through role playing with [name] to ensure that DC's are ready to handle a variety of situations that may present themselves while interacting with older adults in Assisted Living environments. Interviewers will be instructed on methods for determining if a participant becomes distressed during an interview. If this situation occurs, the interviewer will be trained to temporarily discontinue the interview and ask the participant if they wish to terminate the interview and/or to resume at a later time.
- The DSC will coordinate all site-specific training for the DC's.

Measures include:

Demographic Information

Facility

Date entered facility

Ethnicity

Race

Sex

Hearing Handicap for the Inventory – Short Version

Satisfaction with Participation in Discretionary Social Activities – Short Form 7a

Pure Tone Hearing Survey (quietest sound that can be heard at 500, 1000, 2000, 4000 Hz in each ear.

CRFs for these forms are found in the Appendix of the MOP.

Family:

The DSC will send surveys to family members via email or mail depending on what they prefer.

Measure includes:

Zarit Burden Interview -modified 4 question v. 1.0

CRFs for this form is found in the Appendix of the MOP.

Staff:

The DSC will provide paper surveys to the Staff based on the lack of use of email accounts at these locations.

Measure includes:

Michigan Organizational Assessment Questionnaire (MOAQ)

CRFs for these forms are found in the Appendix of the MOP.

No results from the Pure Tone Hearing Survey or the questionnaires for any group will be shared with participants. If a resident is concerned about their hearing, they will be encouraged to see the Audiologist who comes to the facility once per month. This service is always available to them.

Intervention Data

The CF and Audiologist routinely track data for QA and QI as part of their work at UPMC. These data will be used to track the intervention at the individual and facility level. The activities of the CF (described in detail in the MOP) will be recorded in the REDCap database which will allow the Data Survey Coordinator (DSC) to view reports of missing data for each visit. The DSC will follow up with [name] (UPMC Communication Facilitator on the Stakeholder Advisory Panel) if there are missing data on a consistent basis so she can provide re-training to the CF. The Audiologist sees scheduled patients during the monthly audiology visits. We will collect number of visits per facility to track consistency and again, will follow up with the audiologist if there are discrepancies between facilities.

CRFs for the Engage and Consult Model are found in the Appendix of the MOP.

Data related to the complex intervention core functions and forms will be collected and are outlined in the table below.

Problem/Need	Core Functions	Forms (dependent on context, Intermediate individualized)	Outcomes
1. Lack of awareness A. Provide accessible of hearing loss (HL) hearing screening		I. Promote HL awareness and availability of hearing screenings through: a. facility media (digital boards, flyers, etc.)	Within 3 weeks of screening ask resident to describe the results and recommendations (i.e., teach back)
		a. facility media (digital boards, flyers, etc.)	
		b. Letters to residents	
		c. Letters to families	
	B. Provide recommendation to see the Audiologist for a full hearing test	II. Provide screening in central areas and apartments	
		III. Tracking and follow-up to ensure patients receive screening and follow-up hearing tests	Adherence to recommended follow-up audiological exam
		V. Recommend hearing test following a "fail" on hearing screening	Within 3 weeks of testing ask resident to describe the recommendations that were provided at the time of the test (i.e., teach back)
		VI. Schedule hearing test at time of completion of the hearing screening	

2. Lack of knowledge and devices to independently manage hearing loss	A. Creation of Individual Communication Plan	
Ask resident to demonstrate battery removal and re-insertion (this is an direct way to determine that the device has been used device (custom or non-custom) given that the battery would need to be changed) three weeks after receiving the amplification. CF records self-reported and staff-reported use biweekly.

	II. TV device if appropriate	
Ask resident to demonstrate use (turn it on, off, put headset on, etc.) 2 weeks after delivery. CF records self-reported and staff-reported use biweekly.

	III. Amplified Phone Device	
Call resident in order to test ability to use the device successfully. CF records self-reported and staff-reported use biweekly. CF will interact with each resident with a Communication Plan once per week to ensure there is adequate and consistent observation. Staff are assigned to a specific number of residents and therefore

		can provide these observations weekly.
	IV. Communication Strategies	Observation of specific communication strategy use by resident when engaged with the CF (e.g., muting TV when room is entered, looking at speaker, etc.). CF records self-reported and staff-reported use biweekly. CF will interact with each resident with a Communication Plan once per week to ensure there is adequate and consistent observation. Staff are assigned to a specific number of residents and therefore can provide these observations weekly.
3. Lack of Communication Accessibility in the Facility related to group activities	A. Use of sound field equalization (amplification) systems I. Hands on staff training.	Once per month, CF plans timing of facility visit to coincide with planned group activity (e.g., crafts, discussion group, bingo) and record if staff are using room amplification system and if they are passing the microphone to

	different speakers (reinstruct as necessary).
B. Use of group TV amplifying headsets	Once per month, the CF plans timing of facility visit to coincide with group TV activity (movie time, sports event, etc.) and record if staff are offering to assist residents with group TV amplifiers.

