ongoing support to manage technology and the communication environment. An alternative strategy (**Engage Model**) that has shown promise in Senior Living Communities^{7-10,12} consists of this same access to an audiologist but is supplemented by a trained Communication Facilitator (CF) who is available weekly to assist the residents and staff. Assistance provided by the CF may include supporting hearing aids use, troubleshooting technology, dispensing non-custom amplifiers, fostering group communication, and addressing environmental manipulations (**RQ-5**). The Baltimore HEARS study provided a prospective randomized-controlled trial (RCT) designed to assess the feasibility, acceptability, and preliminary efficacy of a hearing intervention including simple amplifiers and ongoing support by CFs in a community-based environment. Although the study included a small number of participants, results indicated that the program was acceptable, 93% benefited, and 100% would recommend the program to others.¹³ An RCT evaluating the Active Communication Education (ACE) program, a chronic care approach, for ARHL found improved hearing-specific HRQoL and increased social participation.¹² Researchers also have focused on other health conditions in RCTs examining the use of support personnel in order to promote ongoing management of chronic conditions and have found reduced disability and improved HRQoL related to the implementation of care assistants.^{37,38} Although encouraging, these results leave a gap in the evidence base that would resolve the dilemma that persists in designing hearing care for ARHL. An intervention study comparing the Consult and Engage Model of hearing health care would assist the resident, family, staff, and organization in decision making related to desired hearing care (**RQ-3**).

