Comparators: The typical pathway to hearing health care includes a self-selected subset of individuals working with an audiologist to obtain hearing aids.⁴⁷ We label this the Consult Model and it represents usual care provided in senior living facilities³⁻⁶. Age-related hearing loss, however, is a chronic condition and may be better served with an ongoing self-management support model (Engage Model)^{8-10,74} supported by a CF who is available to the resident, family, and staff on a weekly basis (two days per week) along with oversight and support from an audiologist who is available virtually to the CF and available to the facility monthly (**RQ-5**).

Expected Outcomes: We hypothesize that Engage Model participants will have significantly greater satisfaction with participation in social activities across residents regardless of hearing status and an increase in hearing-specific HRQoL in residents with hearing loss compared to those receiving the Consult Model. Additionally, we expect to find higher staff satisfaction and lower perceived family burden after stakeholders have experienced the Engage Model as compared to the Consult Model.

Study Design: We propose an open cohort stepped-wedge cluster randomized design (see Table below, **CI-3**) with a phased, randomized roll out (**RQ-2**). The stepped wedge design is a useful design for the evaluation of complex health care interventions⁷⁵ particularly when the intervention is believed to be beneficial with minimal risk.⁷⁶ This design is increasingly being used to evaluate interventions involving health care delivery and has several advantages: (1) allowing the research team and clinical teams to roll out the intervention in a small number of facilities in a timely, systematic manner⁷⁷; (2) possibly increasing participation and buy-in since all facilities will eventually implement the intervention during the study,^{75,78,79} (3) possible increase in statistical power compared to a cluster randomized trial due to increase in data collection and within cluster comparisons.⁷⁵ Our intervention is applied at the facility level (cluster) but the primary outcomes are obtained at the resident level (**RC-1**). In this open cohort design, all residents in a facility are identified to participate but some may leave the facility and others will move into the facility over the course of the study.⁸⁰ (*Criterion 3. Scientific merit*)

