6.3 MEASURES TO MINIMIZE BIAS: RANDOMIZATION AND BLINDING

The study is randomized at the facility level with pairs of facilities randomized to cross over to the intervention. Pairing is not random, rather pairing will be conducted to have comparable N across pairs.

The Data Entry System (REDCap) and Database will be constructed in a manner that will not allow the DCs to determine what intervention is currently present in the building (Consult Model or Engage Model). The DCs will be blinded in this manner but may be unintentionally unblinded by resident comments when they are interacting. The research team does not anticipate needing to unblind data collectors at any point however if necessary, to unblind will be the decision of the PI in consultation with the leadership team. The research team is not blinded due to the need to work with the Data Coordinating Center to implement the Engage Model across the study.

The University of Pittsburgh Physical Therapy Data Center will serve as the Data Coordinating Center (DCC) under the direction of [name] (**IR-7**). We will use an electronic data capture (EDC) system which will be built around standardized case report forms. The system will have additional applications

including participant tracking, file uploads, and reporting. The electronic data management system will allow the trial to be paperless, as all data will be input directly by the research staff into a secure web-based system. Data will be collected on facilities, staff, residents and family members with linkage through unique, study specific identifiers. For residents, the data collected are minimal: demographics, hearing test results, use of hearing devices, satisfaction with social participation, hearing- specific HRQoL, hospitalizations, and change in status such as moving or death. The data core analysts will be blinded to condition (IR-6).

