10.1.8 QUALITY ASSURANCE AND QUALITY CONTROL

The consent process will be monitored with every participant required to provide consent that is tracked in the REDCap data system. Electronic data capture will be monitored by the DSC (described in more detail below). We maintain all source documents to ensure that the electronic data capture mirrors the planned data capture. Data Collection and Intervention Fidelity are monitored on an ongoing basis by the DSC. Protocol deviations will be monitored on a regular basis and dealt with immediately with re-training.

Data Collectors will be trained prior to starting the protocol (see Section 8.1). The DSC will observe each DC in each facility at each data collection time point (Baseline 1, Baseline 2, Time 1, Time 2, Time 3, Time 4). The CRFs related to residents and staff will be captured electronically and directly entered into the REDCap data base built for this study. The Family data will either be electronic (REDCap) survey or returned via paper questionnaire to the DSC who will enter the data. The data from the Audiologist will be provided to the DSC for electronic entry. All routine tracking provided by the CF will be captured directly into the REDCap system. These processes reduce the chance of inaccuracies due to manual data entry from paper records. In addition, this methodology protects participant privacy by reducing paper data sheets. The CFs have standard training through the UPMC Audiology Division. The CF Training Handbook is uploaded as a separate document.

For quality monitoring, the DCC will produce reports for the study team to review that will provide information on 1) consent process, 2) completion of data elements, 3) compliance with intervention, fidelity measures (see section 6.2.1) and 4) protocol deviations.

In addition to reporting, the real-time validation and regular data quality monitoring by the SHRS Data Center are intended to detect and correct errors continuously during the study. Real time validation will be implemented by building data entry fields with restricted options or restricted ranges and data quality prompts upon entry of outlying values. The Data Manager will develop data quality checks, monitor incoming data, and generate queries with specific focus on screening, inclusion/exclusion criteria, randomization, intervention data, outcomes, and adverse events. We will monitor for missing items, missing forms, and range of values entered.

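### The protocol lists the Data Survey Coordinator as a resident data collector and says data collectors are blinded, but the coordinator's own duties reveal which model each facility is in

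*Combined protocol and SAP*

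**What the plan says.** Section 8.1 defines who collects resident data: "DCs will consist of audiology students from the University of Pittsburgh, and the DSC".

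Section 6.3 describes how these collectors are blinded. The data entry system and database "will be constructed in a manner that will not allow the DCs to determine what intervention is currently present in the building". It adds one qualification: "The DCs will be blinded in this manner but may be unintentionally unblinded by resident comments when they are interacting". It then says of the wider group: "The research team is not blinded due to the need to work with the Data Coordinating Center to implement the Engage Model". The DSC is not named in any of these statements, either as an exception to the DC blinding or as a member of the unblinded team.

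Other sections give the DSC these duties:

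- Section 8.1, under intervention data: Communication Facilitator (CF) activities are "recorded in the REDCap database which will allow the Data Survey Coordinator (DSC) to view reports of missing data for each visit". The DSC follows up when CF data are repeatedly missing.
- Section 10.1.8: "All routine tracking provided by the CF will be captured directly into the REDCap system". The same section makes the DSC responsible for continuing oversight of intervention fidelity.
- Section 6.2.1: one block of the fidelity table is restricted to the Engage period. It covers communication plans, amplifiers dispensed and CF presence, among other items.
- Section 6.4: the DSC gathers monthly facility data on the use of group amplification.

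**The concern.** Both primary outcomes, the HHIE and the Satisfaction with Participation form, are residents' own reports. Section 8.4.1 says they are completed as interviews. Residents know what care their building offers, so a collector who does not know the condition is one of the few protections left. It guards against differences in how questions are put, explained or prompted.

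The stated mechanism works through REDCap. For the DSC, REDCap is also where facilitator activity can be seen. Unlike a resident's chance remark, this knowledge comes with the job, and 6.3 does not disclose it.

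Two things are at stake. First, any primary-outcome interview that the DSC conducts after the first crossover is done by someone who knows the condition, whether the facility is then under Engage or still under Consult. Second, a final report that repeats 6.3 would claim a safeguard that does not cover every listed collector.

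**Working it through.** No arithmetic applies. The check sets the sections side by side.

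1. **Is the DSC a data collector?** Yes, by 8.1. The DSC is named alongside the students, and the sentence sets no limit by study period or type of measure.

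2. **Does the blinding statement cover all data collectors?** Yes, by 6.3. It refers to the DCs as a group, and its only stated exception is what residents may say. No section exempts the DSC.

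3. **Do the DSC's duties reveal condition?** They do, by two direct routes.
   - *CF visit reports (8.1, 10.1.8).* Section 2.2 describes Engage as the same audiologist access "supplemented by a trained Communication Facilitator (CF) who is available weekly to assist the residents and staff". Section 6.1.2 describes Consult as a monthly audiologist visit. CF visit records for a facility therefore indicate that it has crossed over. A facility with none expected is still under Consult.
   - *Fidelity monitoring (6.2.1, 10.1.8).* Nobody can track the Engage-only items without knowing which facilities they apply to.

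   The monthly group-amplification data (6.4) point the same way. They are supporting evidence only, because 6.4 does not say that such systems are absent under Consult.

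4. **Does the statement about the research team resolve the conflict?** There are two readings. If the DSC belongs to the unblinded team, the statement that DCs are blinded is false for one of them. If the DSC does not belong to it, the duties in step 3 contradict the statement directly. The sections disagree on either reading.

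5. **When does it matter?** Before the first crossover every facility is under Consult, so knowing the condition separates no facility from another. From the first crossover onward the DSC can tell the two groups apart.

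6. **How many interviews are affected?** The documents do not say. They give neither the DSC's share of resident interviews nor any estimate of interviewer influence. No section describes the DSC actually conducting a resident interview, and none rules it out. Section 8.2 has the DSC at each facility at each time point, so DSC interviewing would be practical.

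**The case against.** The strongest reply is that the point rests on one loosely worded sentence. Straight after naming the DSC, 8.1 describes the collectors as students, and their training includes practice on classmates. Elsewhere the DSC stands apart from the collectors and above them. The DSC trains them and coordinates site training (8.1), checks their conduct on site (8.2), receives their adverse event alerts (8.3.4) and observes them at each round (10.1.8). On that reading the DSC supervises and rarely or never interviews. This stands as a limit on the practical consequence. It does not remove the conflict, because 8.1 names the DSC as a collector and nothing excludes DSC interviews after crossover.

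A second reply is that 6.3 already discloses an unblinded research team. As shown above, placing the DSC in that team confirms the overlap of roles.

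A third reply is that collector blinding is weak in any case. Engage is publicised in the buildings (5.5), a facilitator is on site two days a week (4.1), and collectors work in each building for seven to eight weeks a round (7.3). This also stands in part, since students may learn the condition too. But their knowledge would be incidental and 6.3 partly acknowledges the risk. The DSC's knowledge is built into the role, is not acknowledged and can be avoided.

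A reader might go further and infer that collector blinding fails throughout, or that the primary estimates are biased by some amount. The documents support neither. The conflict is shown for one named role, and both quantities that a bias estimate would need are missing. A reader might also infer that the fault lies in 9.4.2 for having no collector term. That does not follow. A collector main effect would not isolate an interviewer influence that differs by condition, so its absence is not the defect.

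**Conclusion.** Sections 6.3 and 8.1 cannot both be right as written. The DSC is a listed resident data collector, and the DSC's assigned duties disclose facility condition, so the blinding statement does not hold for the DSC. This follows from the text and needs no numerical assumption.

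The size of the consequence is unknown. The number of DSC-conducted outcome interviews after the first crossover may be zero, in which case only the wording is wrong. No magnitude of bias can be stated.

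The point should be corrected because the outcomes are subjective and interview-based and the remedy is cheap. It gives no ground for doubting the design or the primary model. The protocol refers to a Manual of Procedures and a Statistical Analysis Plan as separate documents. If either already keeps the DSC out of these interviews or handles such interviews, only the protocol wording needs to be brought into line.

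**What to change.** **Text changes**

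- In 8.1, state that from the first crossover the student data collectors administer the resident HHIE and Satisfaction interviews. The DSC keeps training, observation, the family and staff surveys, and fidelity monitoring.
- In 6.3, state that the DSC is not blinded to facility condition, and limit the DC blinding statement to the students.

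**Only if DSC-conducted primary-outcome interviews after the first crossover exist or cannot be avoided**

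- Identify them. The REDCap audit trail (10.1.9.1), or the collector's name and visit log left with each resident (5.5), may be enough. Otherwise add one collector field.
- Report their number by condition and assessment round.
- Refit the 9.4.2 model without them as a sensitivity analysis. If there are none, no refit is needed.

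**Cost and limits**

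The cost is two edits, at most one data field, and one conditional refit. Scheduling becomes less flexible. The documents do not give the number of students, so their capacity to cover every interview is an assumption. The refit loses some data and may be selective if DSC interviews were mainly make-up visits for residents who were hard to reach. Residents, and possibly students, will still know the condition, so the change reduces possible interviewer bias without removing it.
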